10.7.4 Split and Merged Target Lesions

The following RECIST v1.1 rules for handling split and merged target lesions are incorporated as part of the data collected on the eCRF;

- If a TL splits in two, then the longest diameters of the split lesions should be summed and reported as the longest diameter for the lesion that split.
- If two TLs merge, then the longest diameter of the merged lesion should be recorded for one of the TL sizes and the other TL size should be recorded as 0 mm.

10.7.5 Change in Method of Target Lesion Assessment

The same imaging technique regarding modality (CT or MRI scan), ideally the same scanner, and the use of contrast should be used in a patient throughout the study to optimise the reproducibility of the assessment of existing and new tumour burden and improve the accuracy of the assessment of response or progression based on imaging.

If a change in method of assessment occurs between CT and MRI, any affected lesions should be treated as missing. When calculating the SOD that includes missing values as a result of a change in assessment method, the scaling rules in Section 10.7.3 will be followed.

10.7.6 Best Percentage Change for Primary Endpoint

Best percentage change from baseline in tumour size will be derived as the largest percentage decrease or the smallest percentage increase in tumour size from baseline.

In order to account for intercurrent events;

- Only values prior to the occurrence of premature study discontinuation or the use of alternative or additional therapy including a new anti-cancer therapy will be considered.
- Where a patient prematurely discontinues treatment, all values will be considered up to the point of PD.
- Where a patient has no evaluable post-baseline assessments, but presents evidence of either death or PD, a value of 20% will be imputed as the best percentage change from baseline. If a log transformation is required for analysis, a value of 0.182321557 will be imputed as the ratio of log(best postbaseline) to log(baseline), which represents a 20% increase when back transformed to the original scale (exp[0.182321557]=1.2).

Note that the BOR in these instances should also be imputed as PD (see Section 10.9.2).

Patients whose data have been imputed will be flagged in listings and waterfall plots where appropriate.

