Progressive Disease (PD)	Appearance of one or more new lesions and/or unequivocal progression of existing non-target lesions			
Non-CR/Non-PD	Persistence of one or more non-target lesion(s) or/and maintenance of tumour marker level above the normal limits			

To achieve "unequivocal progression" on the basis of non-target lesions, there must be an overall level of substantial worsening in non-target disease such that, even in presence of SD or PR in target lesions, the overall tumour burden has increased sufficiently to merit

unequivocal progression by non-target lesions. A modest "increase" in the size of 1 or more non-target lesions is usually not sufficient to qualify for unequivocal progression status. The designation of overall progression solely on the basis of change in non-target disease in the face of SD or PD of target disease will therefore be exceptional.

New Lesions. New lesions not present at baseline should be recorded at time of occurrence.

Overall Response. The overall response is the best response recorded from the start of the treatment until disease progression/recurrence (taking as reference for progressive disease the smallest measurements recorded since the treatment started). For example, a patient who has SD at first assessment, PR at second assessment, and PD on last assessment has a best overall response of PR. In the case of SD, follow-up measurements must have met the SD criteria at least once with a minimum interval of at least 6 weeks from randomisation.

Target Lesions	Non-target Lesions	New Lesions	Overall Response
CR	CR	No	CR
CR	Non-CR/non-PD	No	PR
CR	Not evaluated	No	PR
PR	Non-PD or not all evaluated	No	PR
SD	Non-PD or not all evaluated	No	SD
PD	Any	Yes or No	PD
Not all evaluated	Non-PD	No	NE
PD	Any	Yes or No	PD
Any	PD	Yes or No	PD
Any	Any	Yes	PD

CR=complete response; NE=not evaluable; PD=progressive disease; PR=partial response; SD=stable disease.

Duration of Response. The duration of overall response is measured from the time measurement criteria are met for CR or PR (whichever is first recorded) until the first date that recurrent or progressive disease is objectively documented (taking as reference for progressive disease the smallest measurements recorded since the treatment started). Stable disease is measured from the start of the treatment until the criteria for progression

are met, taking as reference the smallest measurements recorded since the treatment started.

Response review

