Treatment with pembrolizumab will continue until: RECIST v1.1-defined disease progression is determined by the investigator (Eisenhauer et al 2009), unacceptable toxicity, or a maximum of 24 months. If progression is suspected, but not confirmed, study treatment may continue until confirmation of radiological progression. Treatment with setanaxib or placebo will continue throughout the period of pembrolizumab therapy. When pembrolizumab is discontinued, blinded study treatment will also be discontinued.

Baseline assessments will be performed on Day 1 (Visit 2). Post-Baseline assessments will be performed every 3 weeks up to pembrolizumab discontinuation. Following permanent IMP discontinuation at any time during the study, patients will undergo an End-of-Treatment (EoT) Visit as soon as possible and a Safety Follow-up Visit at 28 days after the last dose.

Initial tumour imaging is performed within 35 days prior to the date of treatment and will be used as the Baseline scan for the tumour assessments. Tumour assessments will then be conducted from the date of randomisation and continue until RECIST v1.1-defined disease progression, irrespective of treatment discontinuation. Efficacy Follow-up for PFS and survival will continue until approximately 38 progression events have occurred. AEs will be recorded up to 28 days after study treatment discontinuation, while any further anti-cancer medication will be recorded until disease progression.

The primary endpoint is best percentage change in tumour size. A population with measurable disease will be selected to generate the maximum tumour response data. The secondary endpoints related to numbers of CAFs, CD8⁺ TILs, and regulatory T-cells in tumour tissue, and gene expression analysis in tumour tissue will be used to demonstrate the underlying mechanisms of action of setanaxib and support the primary objective.

Safety and tolerability data will be regularly reviewed by an unblinded IDMC, with the first assessment after approximately 12 patients (6 per treatment group) have had the opportunity to complete at least one cycle of pembrolizumab +/- setanaxib, followed by periodic assessments at a frequency defined in the IDMC Charter. The IDMC may recommend changes to the setanaxib dose regimen or study conduct based on the safety data reviews.

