9.1 Estimand Attributes

9.1.1 Primary Estimands

Primary Objective	Primary Estimand Attributes	
• To compare the change in tumour size per RECIST v1.1 in recurrent or metastatic SCCHN patients treated with setanaxib and pembrolizumab versus patients treated with placebo and pembrolizumab	 Treatment: setanaxib + pembrolizumab versus placebo + pembrolizumab. Population: Patients in the FAS who also have measurable disease at baseline. 	
	Variable:	
	Best percentage change in tumour size defined as the percentage change from Baseline in the sum of diameters of target lesions, as assessed by RECIST v1.1.	

Intercurrent Events:
1. Premature study discontinuation
2. Use of certain alternative or additional therapy including a new anti- cancer therapy
3. Premature study drug discontinuation/interruption
4. PD or Death
• Strategy: Hybrid (While on Treatment / Treatment Policy / Hypothetical)
A While on Treatment approach will address the first 2 intercurrent events listed above. Any values for the variable of interest after the occurrence of either of the first 2 intercurrent events listed are considered irrelevant in defining the treatment effect of interest, i.e. only values prior to the occurrence of the intercurrent event are considered.
A Treatment Policy approach will be taken where a patient prematurely discontinues treatment, i.e. all data will be used up to the point of PD.
A hypothetical approach will be taken where a patient has no evaluable post-baseline assessments, as a result of PD or death, by performing imputation (See Section 10.7.6).
Population Level Summary Measure:
The LS Mean difference (or geometric mean ratio if a log transformation has been applied), 80% CI and associated p-value for the treatment comparison will be obtained from the ANCOVA model.

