10.9.2 Best Objective Response

The BOR is selected as the best response of the individual programmatically derived overall visit responses, in sequential order from are CR, PR, SD*, PD and not evaluable (NE),

* Note that for SD, the patient must be stable at or after the first scheduled scan at 9 weeks (+/- 1 week). If an unscheduled scan is conducted prior to the week 9 assessment and shows SD, it will be listed but not included in the summary of BOR.

In cases where an overall visit spans multiple days, determination of the date on which the BOR occurred will follow these rules;

- For SD, the earliest of the dates contributing towards the overall visit assessment will be used.
- For CR or PR, the latest of the dates contributing towards the overall visit assessment will be used.

In order to account for intercurrent events;

- Only values prior to the occurrence of premature study discontinuation or the use of alternative or additional therapy including a new anti-cancer therapy will be considered.
- Where a patient prematurely discontinues treatment, all values will be considered up to the point of PD.

In cases where a patient has no evaluable post-baseline assessments, but presents evidence of either death or PD, the BOR will be imputed as PD.

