10.9.4 Duration of Response

The DoR is defined as the number of days from the date of first documented CR or PR until the date of first documented PD or death in the absence of PD, whichever is earlier. The number of patients in the FAS with measurable disease at baseline and had a best overall response of CR or PR, will be used.

DoR(days) = (Earliest Date of PD or Death - Earliest Date of CR or PR) + 1

If a patient does not experience PD following an initial CR or PR, then the corresponding DoR will be censored using the same rules defined for PFS (See Section 10.8.1).

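### SAP 10.7.6 and 9.1.1 set no progression cut-off for the primary endpoint in patients still on treatment, and 10.9.2 conflicts with 9.1.2 on the same point

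*SAP*

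**What the plan says.** **Primary endpoint.** SAP 10.7.6 defines it as the greatest shrinkage or, where there is none, the least growth relative to the baseline scan. The definition has no progression limit of its own. Three rules follow:

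- For everyone, values stop counting at study discontinuation or at alternative or additional therapy.
- "Where a patient prematurely discontinues treatment, all values will be considered up to the point of PD".
- A patient with no evaluable post-baseline scan but with evidence of PD or death is given +20%.

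**Primary estimand.** SAP 9.1.1 lists PD or death as the fourth intercurrent event. Its strategy for that event is: "A hypothetical approach will be taken where a patient has no evaluable post-baseline assessments, as a result of PD or death". The phrase "all data will be used up to the point of PD" appears only in the sentence about patients who discontinue treatment prematurely.

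**Response.** SAP 10.9.2 states: "The BOR is selected as the best response of the individual programmatically derived overall visit responses". It then repeats the discontinuation-only PD rule. The ORR/DCR estimand in SAP 9.1.2 is different: PD or death is among three events handled by a while-on-treatment strategy, and only earlier values count, for every patient. Protocol Appendix IV agrees: "The overall response is the best response recorded from the start of the treatment until disease progression/recurrence".

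**Conduct.** SAP 8.0: "If progression is suspected, but not confirmed, study treatment may continue until confirmation of radiological progression". Protocol 5.2.1.2 lets patients continue to the next scheduled assessment when progression is uncertain, and keeps imaging going until the investigator confirms radiological progression. SAP 10.9.1 re-derives the overall visit response by program.

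**The concern.** Best percentage change takes the most favourable value in the eligible window, so the end of that window matters. For a patient with evaluable scans, the only progression limit is attached to stopping treatment early. Whether shrinkage after PD counts in the primary endpoint therefore depends on treatment status at the time of analysis.

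Treatment status is a post-randomisation outcome that the study drug could affect. IMP is interrupted, and may be stopped, under the anaemia and TSH rules in Protocol 5.3.2.1 and 5.3.2.2. The rule is also unstable over time, because a patient on treatment at one data cut-off may have stopped by the next. In addition, Protocol 4.3.1 does not name progression among its reasons for premature discontinuation, so it is unclear whether stopping for PD brings the cut into force.

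For response, a programmer following 10.9.2 and one following 9.1.2 could assign different best responses to the same patient. SAP 12.5.2.3 plans no sensitivity analysis of the primary endpoint, and the per-protocol repeat is not designed to show this effect.

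**Working it through.** **1. The plan's own design figure.** Inputs from SAP 8.1: 25 per arm, difference 20 points, SD 30, two-sided alpha 20%.

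- Standard error of the difference = 30 × √(2/25) = 8.485.
- Normal approximation: 20/8.485 = 2.357; 2.357 − 1.282 = 1.075; power 85.9%.
- Exact noncentral t with 48 df: 85.4%.

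The stated 85% reproduces. The point concerns a derivation rule, so this only confirms the yardstick.

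**2. The rules side by side**, for a patient with evaluable scans after a first derived PD and no new therapy:

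| Source | On treatment at cut-off, or completed treatment | Stopped early |
|---|---|---|
| 10.7.6 and 9.1.1, best % change | no PD cut stated | cut at PD |
| 10.9.2, best response | no PD cut stated | cut at PD |
| 9.1.2, ORR and DCR | values before PD only | values before PD only |
| Protocol Appendix IV, best response | ends at progression | ends at progression |

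The first row is a gap with nothing elsewhere to close it. The second row conflicts with the third and fourth.

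**3. Worked example (assumed measurements).** Sum of diameters is 100 at baseline, 125 at Week 9 (Day 64) and 65 at Week 15 (Day 106); target days are from SAP Table 1.

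- Week 9: (125 − 100)/100 = +25%, above the 20% PD threshold.
- Week 15: (65 − 100)/100 = −35%.
- Literal 10.7.6, still on treatment: best change −35%. Stopped early, or a PD cut for all: +25%.
- Swing: 25 − (−35) = 60 points. Effect on the mean of an arm of 25: 60/25 = 2.4 points, and 2.4/20 = 12% of the design difference.

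**4. Same scans, two analyses.** If this patient is on treatment at the primary cut-off and stops early afterwards, the value is −35% in the primary ANCOVA and +25% in the updated waterfall plot that SAP 12.5 provides for.

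**5. Range.** The documents give no count of such patients. Shift in the difference = k × g/25, where k is the excess of affected patients in one arm and g the points gained by each.

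- k = 0: no change.
- k = 1, g = 10: 0.4 points.
- k = 1, 2, 3 with g = 60: 2.4, 4.8, 7.2 points.

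With no true effect and SD 30, noncentrality = shift/8.485. The nominal 20% two-sided error becomes about 20.0% at 0.4 points, 21.8% at 2.4, 26.8% at 4.8 and 34.7% at 7.2. The upper end needs three large swings, all in one arm.

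**The case against.** **A reader might infer that the SAP counts responses after progression.** Taken alone, 10.9.2 would make the example patient a PFS event on Day 64 and a partial responder on Day 106. It would move ORR in that arm by 1/25 = 4 points. The formula in 10.9.4, "DoR(days) = (Earliest Date of PD or Death - Earliest Date of CR or PR) + 1", would then return 64 − 106 + 1 = −41 days. The documents do not support this as the plan's rule. SAP 9.1.2 limits ORR and DCR to values before PD for all patients, Appendix IV ends best response at progression, and 10.9.4 speaks of progression following a first response. What stands is that 10.9.2 needs aligning.

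**A reader might also infer that everyone treated past PD escapes the cut.** That goes too far. Someone who later stops early has also discontinued prematurely, and on that reading is cut at PD. Only patients still on treatment at the cut-off, or who complete it, fall in the gap.

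**The exposed group is small.** Treatment and scans are planned to end at RECIST progression. The programmatic visit response combines site-recorded target, non-target and new-lesion entries, so a derived PD ahead of the investigator's arises mainly when a site's overall call disagrees with its own components. If the site records no PD component, later scans are not post-PD at all. This stands and limits the size. It does not remove the group, because the plan allows treatment and imaging to continue past a suspected PD.

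**The intent may be benign.** The bullet may only mean that stopping treatment is not itself a cut-off, with a PD limit assumed for everyone. That is plausible, but neither 10.7.6 nor 9.1.1 says it. Appendix IV cannot supply it, since it defines best response and not best percentage change.

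**Bias needs imbalance.** The trial is double-blind, and equal numbers with equal swings in both arms would leave the difference unchanged. That is correct; the figures for the treatment difference above are conditional on imbalance.

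**Conclusion.** The point holds for the primary endpoint. As written, the PD cut-off depends on premature treatment discontinuation, and PD as an intercurrent event is handled only when there is no evaluable scan. Values after a first derived PD therefore count for some patients and not for others, and can change between analyses. For response the point is narrower: 10.9.2 is inconsistent with 9.1.2 and Appendix IV.

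The likely size is small. Assuming 0 to 3 affected patients and a 60-point swing each, the shift in an arm mean is 0 to 7.2 points, or 2.4 per patient. Both the count and the swing are assumptions, and with no such patients nothing changes. Because this is the primary endpoint, the programmer should not have to choose the rule.

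**What to change.** In SAP 9.1.1, 10.7.6 and 10.9.2, replace the discontinuation-only wording with: *For all patients, on or off treatment, values up to and including the first derived PD visit are used (subject to the earlier cut at study discontinuation or new anti-cancer therapy); later values are listed only.*

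In SAP 9.1.2, change the ORR/DCR restriction, which admits only values before PD, to the same form. Otherwise the edit leaves a new mismatch over whether the PD visit itself counts.

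The cost is one sentence in three places and a matching edit in a fourth. It needs no new data and does not change sample size or power. The downside is that shrinkage after pseudo-progression is listed and not counted. For best response that agrees with Appendix IV; for best percentage change it is a choice that the SAP should state openly.

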8.4.4 Sensitivity Analysis

The proportionality of hazard will be examined in the sensitivity analysis for the fitted Cox proportional hazard model for PFS using the cumulative sums of martingale residuals for each treatment groups. The ASSESS statement with ODS Graphics in PROC PHREG step in SAS will perform this using both graphical and numerical methods of Lin, Wei, and Ying 1993 (Lin et al 1993). A violation of the proportional hazard assumption will indicate that the results obtained from the fitted Cox proportional hazard model will be invalid. In such circumstances, a modified max combo (Roychoudhury et al 2021) using the Fleming and Harrington 1981 weights (Fleming & Harrigton 1981) such as FH(0,0), FH(0.5,0.5), FH(0,0.5), FH(0.5,0) will be implemented for estimating the performance of the competing treatment groups for PFS. The p-value obtained from each of the modified max combo tests will be reported.

For each of the fitted ANCOVA models in the primary efficacy analysis and the secondary efficacy analyses, a plot of the residuals against the fitted values from the ANCOVA model will be produced to check for randomness in the plot. This is to check for the assumption of constant variance of the fitted model. Any systematic effect in this residual plot will indicate that a suitable transformation should be applied on the response of the model as appropriate to stabilise the variability of the error. A normal probability plot will also be plotted of the residuals of each of the fitted ANCOVA model to check if this fairly fits a straight line. Significant deviation from a straight line in this residual plot will indicate the violation of the ANCOVA model assumptions of the errors being normally distributed. In such cases, logarithmic transformations on the response will be applied, as appropriate, to normalise the data. The ANCOVA in such scenario will be fitted again on the log-normal response with log baseline values as the covariate, and the validity of the assumption of the fitted ANCOVA is the post-dose baseline ratio. If the assumptions

are not satisfied for the fitted transformed model, appropriate non-parametric method will be applied. Further details will be provided in the SAP.

The analysis of the primary endpoint will be repeated on the Per-Protocol Analysis Set to understand the effect of major protocol deviations on the treatment effect.

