10.0 Conventions and Derivations

10.1 Baseline, Change and Percent Change from Baseline

Baseline is defined as the last non-missing value before the first dose of IMP. Baseline values will generally be assessed at the Day 1 visit, the exception to this is the Initial tumour imaging scan which will be performed within 35 days prior to the date of treatment and will be used as the Baseline scan for the tumour assessments. For re-screened patients, the value associated with their screen failure record will not be considered for baseline.

If time of assessment is not collected and the assessment is collected on the same date as the first dose, the assessment will be assumed to be per protocol, i.e. prior to first dose. If multiple continuous assessments occur on the same day as first dose and no time is recorded, the average value will be used as baseline.

Change from baseline at any post-baseline time point will be defined as:

- Absolute Change from Baseline = (Value at Post Baseline Time Point Value at Baseline)
- Ratio of Postbaseline to Baseline = $\left(\frac{Value \ at \ Post \ Baseline \ Time \ Point}{Value \ at \ Baseline}\right)$

Percentage change from baseline at any post-baseline time point will be defined as:

• Percentage Change from Baseline = $100 * \left(\frac{Value \ at \ Post \ Baseline \ Time \ Point-Value \ at \ Baseline}{Value \ at \ Baseline}\right)$

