12.5.2.2 Primary Analysis

The primary efficacy analysis will evaluate the effect of setanaxib on the best percentage change in tumour size using an ANCOVA model, including covariates for treatment, baseline tumour size and the randomisation stratification HPV status (if there are at least 10 subjects at each level within each treatment group).

The number of patients, unadjusted mean, and adjusted least squares (LS) means for each treatment group will be presented, together with the difference in adjusted LS means, 80% and 95% CIs and corresponding p-value from the fitted ANCOVA model.

A plot of the residuals against the fitted values will be produced to check the assumption of constant variance. Any systematic effect in this residual plot along will indicate that a suitable transformation (log transformation) should be applied on the response of the model as appropriate to stabilise the variability of the error.

A normal probability plot will also be plotted of the residuals of the fitted ANCOVA model in addition to a Shapiro-Wilk test, used to test for the distribution of normality of the residuals. If the normal probability plot shows a concave curve of the residuals against the normal quantiles along with the p-value obtained from the Shapiro-Wilk test being less than 0.05, then this indicates a violation of the ANCOVA model assumption of the errors being normally distributed.

If the ANCOVA model assumptions are not upheld, logarithmic transformations on the response will be applied to normalise the data. The log(post-baseline) to log(baseline) ratio will be analysed using an ANCOVA model, including covariates for treatment, log-transformed baseline tumour size and the randomisation stratification HPV status.

The number of patients, unadjusted geometric mean, and adjusted geometric LS means for each treatment group will be presented, together with the difference in adjusted geometric LS means, 80% and 95% CIs and corresponding p-value from the fitted ANCOVA model.

The validity of the assumptions of the fitted transformed model will be checked similarly.

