If the assumptions are not satisfied for the log-transformed model, a non-parametric method will be performed using a Ranked ANCOVA (Quade D. [1967]). A linear regression of the ranks of the best percentage change from baseline based on the ranks of the covariate for baseline tumour size and HPV status fitted as a class variable (ignoring treatment). The residuals from this regression model will then be analysed using an ANOVA model with treatment as the independent variable. The resulting p-value from the F test of this ANOVA will be reported.

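### The log-scale fallback for the primary endpoint is defined as log(post) divided by log(baseline), but its imputed value and geometric mean ratio hold only for log(post/baseline)

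*SAP*

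**What the plan says.** **Imputed value (SAP 10.7.6).** A patient with death or PD and no evaluable post-baseline assessment receives +20% as best percentage change. If the log model is used, 0.182321557 is "imputed as the ratio of log(best postbaseline) to log(baseline), which represents a 20% increase when back transformed to the original scale (exp[0.182321557]=1.2".

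**Model response (SAP 12.5.2.2).** "The log(post-baseline) to log(baseline) ratio will be analysed using an ANCOVA model", with treatment, log baseline tumour size and HPV status as covariates. The report gives geometric LS means by group, "together with the difference in adjusted geometric LS means, 80% and 95% CIs and corresponding p-value".

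**Summary measure (SAP 9.1.1).** "The LS Mean difference (or geometric mean ratio if a log transformation has been applied), 80% CI and associated p-value".

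**Related definitions.** SAP 10.1 defines "Ratio of Postbaseline to Baseline" on raw values, without logs. Protocol 8.4.4 says "The ANCOVA in such scenario will be fitted again on the log-normal response with log baseline values as the covariate"; the rest of that sentence mentions a post-dose to baseline ratio but is garbled.

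**Trigger and next step (SAP 12.5.2.2).** One trigger reads "If the normal probability plot shows a concave curve of the residuals against the normal quantiles along with the p-value" from a Shapiro-Wilk test being below 0.05. The other is a systematic pattern in the residual plot. If the log model also fails, a ranked ANCOVA on percentage change follows: "The resulting p-value from the F test of this ANOVA will be reported".

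**The concern.** Two different quantities are in play. One is the log of a ratio, log(post/baseline), which is 0 for no change and exponentiates to a fold change. The other is a ratio of logs, log(post)/log(baseline), which is 1 for no change and has no such interpretation. The constant, its back-transformation and the geometric mean ratio belong to the first. The two SAP sections that define the response name the second.

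If the text is programmed as written, two things can go wrong in the primary analysis. A patient with the worst outcome enters the log model as one of the best. And even with no such patient, the exponentiated treatment effect is not a geometric mean ratio and is pulled towards 1. Separately, 12.5.2.2 reports a difference of geometric LS means where the estimand in 9.1.1 names a ratio.

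**Working it through.** **Inputs.** The constant 0.182321557 and its claimed meaning (+20%, exp = 1.2) are from SAP 10.7.6. The response definition is from SAP 12.5.2.2. Group size 25 is from SAP 8.1. The documents give no distribution of baseline sums of diameters, so b = 10, 50 and 200 mm is assumed; 10 mm is the smallest measurable non-nodal lesion in Protocol Appendix IV.

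**1. The plan's own figure.** ln(1.2) = 0.1823216 and exp(0.182321557) = 1.2000. It reproduces, as the natural log of post/baseline for a 20% increase.

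**2. The response as written.** log(post)/log(b) = 1 + ln(post/b)/ln(b). A 20% increase is therefore 1 + 0.18232/ln(b). No change is 1 at every baseline, and exp(1) = 2.72 rather than 1.00.

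**3. What the imputed value means on that scale.** Setting log(post)/log(b) = 0.18232 gives post = b^0.18232.

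**4. Treatment effect with no imputed patient.** With a common baseline the difference in means is ln(GMR)/ln(b). For a true geometric mean ratio (GMR) of 0.80, ln(0.80) = -0.22314.

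| Assumed baseline b | 10 mm | 50 mm | 200 mm |
|---|---|---|---|
| Written response for +20% | 1.079 | 1.047 | 1.034 |
| Size implied by 0.18232 | 1.52 mm | 2.04 mm | 2.63 mm |
| Implied change (intended: +20%) | -84.8% | -95.9% | -98.7% |
| Difference for true GMR 0.80 | -0.0969 | -0.0570 | -0.0421 |
| Its exponential | 0.908 | 0.945 | 0.959 |
| Apparent reduction (true: 20%) | 9.2% | 5.5% | 4.1% |

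**5. One imputed placebo patient among 25**, the other 24 unchanged and all setanaxib patients at 0.80.
- Correct scale: exp(ln 0.8 - ln 1.2/25) = exp(-0.22314 - 0.00729) = 0.794.
- As written: placebo mean = (24 + 0.18232)/25 = 0.9673. The setanaxib mean is 1 plus the difference in the table. The group differences are -0.0642, -0.0243 and -0.0094, and their exponentials 0.938, 0.976 and 0.991.

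**6. Units.** The written response also depends on the unit of measurement. A 20% increase from 50 mm is ln(60)/ln(50) = 1.047 in mm, but ln(6)/ln(5) = 1.113 in cm. The log of the ratio is 0.182 in both.

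**7. Varying baselines with the log-baseline covariate.** Step 4 holds baseline fixed. An illustrative simulation lets it vary (25 per arm, median baseline 60 mm, log-SD 0.5, mean change -10% versus -30%, SD 30%, 4,000 runs, no imputed patient). The mean exponentiated coefficient was 0.744 on the correct scale and 0.927 as written. The chance of p<0.2 favouring setanaxib was 0.81 on both. Without imputed patients the damage is to the estimate, not the test.

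**The case against.** **The intent is clear.** The sentence in 10.7.6 carries its own check, which only log(post/baseline) satisfies. SAP 9.1.1 names a geometric mean ratio, SAP 10.1 defines the ratio on raw values, and the zero-replacement rule in 12.5.2.1 is written for that plain ratio. All of this is right and shows which reading to adopt. It does not make the two defining sentences correct.

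**The mistake would show.** Coded as written, the required geometric group means come out at about 2.3 to 2.7 (changes from -30% to none at the assumed baselines). That is apparent growth beside a waterfall plot showing shrinkage. This makes detection likelier, but the plan should not rely on it.

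**The rank step protects the result.** Largely true for the test. In an illustrative simulation with one imputed placebo patient, under the assumptions of step 7 apart from that patient, Shapiro-Wilk on the written response gave p<0.05 in all 2,000 runs; the plot must still be judged by eye. The analysis would then pass to ranks of percentage change, which use the correct +20%. The figures in step 5 therefore apply only if the log model is kept. But the rank step reports only a p-value, so the estimate and CI named in 9.1.1 would be lost.

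**The size mixes readings.** Steps 4 and 5 exponentiate the LS-mean difference, as 9.1.1 implies. Taken literally, 12.5.2.2 would subtract geometric LS means. With placebo unchanged, that is 2.718 × (0.908 - 1) = -0.25 at 10 mm, and -0.15 and -0.11 at 50 and 200 mm. That is fair, and it shows that 12.5.2.2 does not deliver the estimand's summary measure on either reading.

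**Nothing shows literal coding.** Correct. The table shells and programs are not among these documents, so the harm is conditional.

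**Conclusion.** The concern holds. The constant is right and the named response is wrong, in both SAP sections that define the log-scale primary response. Followed exactly, the rule codes death or progression without a scan as shrinkage of 85% to 99% instead of a 20% increase. It also reports a true 20% relative reduction as one of 4% to 9%.

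These sizes rest on assumed baseline sums of 10 to 200 mm, and the treatment-effect figures on a common baseline. They apply only if the log fallback is used and coded as written and, for the treatment-effect estimates, if that model is kept. How often the fallback would be used cannot be worked out from the documents, because both plots are judged by eye. Sample size and the main untransformed analysis are unaffected. Since this is the first prespecified fallback for the primary endpoint and part of its estimand, it should be corrected.

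**What to change.** - In SAP 10.7.6 and 12.5.2.2, define the log-scale response as log(best post-baseline sum of diameters / baseline sum of diameters), in line with the ratio in 10.1.
- Keep 0.182321557 as the imputed value and log baseline as the covariate.
- In 12.5.2.2, replace the difference in adjusted geometric LS means by the exponentiated LS-mean difference with its 80% and 95% CIs, labelled as the geometric mean ratio of 9.1.1.
- Confirm that the analysis programs follow this definition.

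The cost is two or three SAP sentences and a check of the code. No data, sample size or timeline changes.
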